### **Purposes for Amendment 4**

The purposes of this amendment are to:

- Allow sites' determination of positron emission tomography (PET) positivity to guide additional radiotherapy for noncomplete responders at the conclusion of frontline therapy, allow radiation to be given for patients with PET-positive residual masses of any size instead of only those with masses of 2.5 cm or larger, and allow sites to select radiation doses as medically appropriate.
- Specify Mosteller's nomogram for calculating BSA
- Require only seated measurements of blood pressure
- Align progressive multifocal leukoencephalopathy (PML) descriptive text across the sponsor's clinical protocols
- Clarify that sites need not perform Deauville assessments of PET scans, which will be performed by an independent review facility
- Specifically describe the recording of data regarding the incidence PML or malignancies other than classical Hodgkin lymphoma (HL), data regarding a switch in frontline therapy, and data regarding unscheduled bone marrow or cytology results
- Remove specific limits on blood sampling volumes for serum biomarkers, immunogenicity, and germline DNA to accommodate small variations among sampling kits
- Remove patient decision as a reason for discontinuing study drug as it is already a reason for study withdrawal
- Clarify that, unless otherwise specified, only those serious adverse events that occur during long term follow-up that are considered related to study drug (instead of "frontline therapy") will be reported.
- Further clarify that pregnancy data will be collected until study closure
- Correct typographical errors, punctuation, grammar, and formatting.

## **15.12 Amendment 5 Rationale and Purpose**

### **Rationale for Amendment 5**

Amendment 5 seeks to eliminate a potential bias in favor of the experimental treatment arm by providing symmetry across the 2 treatment arms in the definition of completion of frontline therapy, which might affect the modified progression-free survival (mPFS) primary endpoint of the study. The amendment also contains minor updates to enhance patient safety, improve protocol clarity and compliance, and align study conduct with the sponsor's current guidelines and practices.

### **Purposes for Amendment 5**

The purposes of this amendment are to:

- **Provide symmetry across the 2 treatment arms in the definition of completion of frontline therapy:**
  - Standardize the definition of a missed dose across the 2 treatment arms to permit investigators, who are best able to determine the adequacy of the delivered regimen and the need to make adjustments for treatment-related toxicity, to omit individual agents from the randomized treatment regimen without this counting as a missed dose.
- **Enhance patient safety:**
  - Add acute pancreatitis and hepatotoxicity to the discussion of potential risks associated with brentuximab vedotin.
  - Require consultation with the contract research organization (CRO) and/or sponsor's project clinician as prerequisite for changing the order of administration of the study drugs and specify that the order of administration must not be changed for the subset of patients from whom additional pharmacokinetic (PK) samples are to be obtained.
  - Permit the prophylactic use of antiemetics during the treatment period of the study.
  - Allow for the use of alternate methods other than the Mosteller formula standard nomogram for the calculation of body surface area (BSA) to ensure that sites using electronic chemotherapy order entry systems are able to comply with the protocol. Electronic chemotherapy order entry systems enhance patient safety by eliminating the potential for manual calculation errors, and should be supported where available.
- **Institute minor modifications in study procedures to enhance clarity and/or facilitate greater compliance with the protocol:**
  - Clarify that the abbreviated version of Functional Assessment of Cancer Therapy-Neurotoxicity (FACT-Ntx Abbreviated) is being used in the study.
  - Revise the anticipated number of study sites globally.
  - Clarify the exclusion criterion pertaining to pulmonary diffusion capacity.
  - Clarify the procedure for supply of study drugs.
  - Clarify the guidelines for reconstitution and disposal of brentuximab vedotin.

## **Brentuximab vedotin (ADCETRIS®)**

### **Clinical Study Protocol C25003 Amendment 7, EudraCT: 2011-005450-60**

- Clarify the accountability requirements for bleomycin.
- Remove the requirement for body temperature to be measured orally.
- Align the pregnancy testing guideline with that in the Schedule of Events.
- Clarify the guidelines for preparation of unstained slides of tumor tissue to be used for assessment of biomarkers to reflect current practice at some diagnostic facilities.
- Clarify posttreatment follow-up assessments for patients who do not complete 6 treatment cycles.
- Clarify the guideline for posttreatment follow-up assessments for mPFS.
- Stipulate fasting for patients before measurement of blood glucose concentrations; remove the requirement for the patient to fast before measurement of hemoglobin A1C (Hb A1C) concentrations and revise the timing of these measurements to optimize the clinical value of these measurements.
- Specify that posttreatment patient-reported outcomes (PRO) assessments will not be performed by telephone.
- Clarify the timing between screening and administration of first dose of study drugs.
- Clarify that a computed tomography (CT) scan must be performed when patients start an alternate therapy before completion of the randomized treatment regimen (either A+AVD or ABVD).
- **Align study conduct with the sponsor's current guidelines and practices:**
  - Modify contraception language.
  - Define peripheral neuropathy (PN) and PN-related adverse events (AEs) and align the monitoring guidelines for these AEs across the brentuximab vedotin clinical development program.
  - Update the reporting period for serious adverse events (SAEs) to Millennium from 1 working day to 24 hours.
  - Update SAE reporting language to meet regulatory requirements in the European Union (EU) Directive, 2001/20/EC Article 17 parts (a) and (b).
  - Clarify the monitoring and reporting guidelines for treatment-related AEs.
  - Update text pertaining to product complaints and medication errors for commercial products.
  - Revise and update the Serious Adverse Event and Pregnancy Contact Information.
- **Correct typographical errors, punctuation, grammar, and formatting.**

For specific examples of changes in text and where the changes are located, see Section [15.13](#).

## **15.13 Amendment 6 Rationale and Purpose**

### **Rationale for Amendment 6**

Amendment 6 removes the exclusion criterion pertaining to pulmonary diffusion capacity on the basis of input from study investigators and the study's Steering Committee to better align with standard practice in the treatment of patients with advanced classical Hodgkin lymphoma (HL) and increase the generalizability of the study. Pulmonary carbon monoxide diffusion capacity (DLCO) does not accurately reflect pulmonary reserve, particularly in patients with advanced HL who may have mediastinal and/or pulmonary involvement. Patients who have been excluded from this study on the basis of DLCO have generally been treated with ABVD (doxorubicin [Adriamycin], bleomycin, vinblastine, and dacarbazine), indicating that the exclusion criterion does not reflect current standard practice.

The amendment also contains revised and updated serious adverse event (SAE) reporting contact information.

### **Purposes for Amendment 6**

The purposes of this amendment are to:

- Remove the exclusion criterion pertaining to pulmonary diffusion capacity
- Revise and update the SAE Reporting Contact Information to reflect the change in the sponsor's vendor
- Correct typographical errors, punctuation, grammar, and formatting

For specific examples of changes in text and where the changes are located, see Section [15.14](#).

## **15.14 Amendment 7 Detailed Summary of Changes**

THE PRIMARY SECTIONS OF THE PROTOCOL AFFECTED BY THE CHANGES IN AMENDMENT 7 ARE INDICATED. THE CORRESPONDING TEXT HAS BEEN REVISED THROUGHOUT THE PROTOCOL.

---

**Purpose:** Increase study enrollment.

- Increase the sample size by 200 patients to a total of approximately 1240 enrolled patients, and increase the anticipated enrollment period.

The primary change occurs in Section [4.1, Overview of Study Design](#):

Formerly read: The study will enroll approximately ~~1040~~ patients; enrollment is anticipated to last ~~2~~ years.

---

Now reads: The study will enroll approximately **1240** patients; enrollment is anticipated to last **3** years.

Sections that also contain this change are:

- Section [4.2, Number of Patients](#)
  - Section [8.1.1, Determination of Sample Size](#)
  - [Protocol Summary](#)
- 

- Increase enrollment to 620 patients per treatment arm, and increase the estimated number of sites to 250 study sites globally.

The primary change occurs in Section [4.2, Number of Patients](#):

Formerly read: Approximately ~~1040~~ patients (approximately ~~520~~ patients per treatment arm) will be randomized in this study from approximately ~~200~~ study centers globally, ~~including centers in North America, Europe, and Asia.~~

---

Now reads: Approximately **1240** patients (approximately **620** patients per treatment arm) will be randomized in this study from approximately **250** study centers globally.

Sections that also contain this change are:

- Section [4.1, Overview of Study Design](#)
  - [Protocol Summary](#)
-

- Delete reference to the percentage of the original sample size that was planned for inclusion in the interim futility analysis.

The primary change occurs in Section [4.1, Overview of Study Design](#):

Deleted text: An interim futility analysis will be conducted when the first approximately 348 patients (~~1/3 of overall sample size of 1040 patients~~) have completed the regimen to which they were randomized (ie, received the planned study drug regimen with no more than 2 missed doses of A+AVD or ABVD) or have discontinued treatment prior to completion.

Section [8.1.10, Interim Analyses](#) also contains this change.

---

- Revise the projected length of enrollment and follow-up periods.

The primary change occurs in Section [4.3, Duration of Study](#):

Formerly read: It is expected that the study will last approximately 60 months to reach the final analysis of the mPFS endpoint (approximately ~~24~~ months of enrollment plus ~~36~~ months of additional follow-up after the last patient is randomized).

Now reads: It is expected that the study will last approximately 60 months to reach the final analysis of the mPFS endpoint (approximately **36** months of enrollment plus **24** months of additional follow-up after the last patient is randomized).

Sections that also contain this change are:

- Section [8.1.1, Determination of Sample Size](#)
  - [Protocol Summary](#)
- 

**Purpose:** Revise the statistical assumptions of mPFS rates for both treatment arms in the study.

The change occurs in Section [8.1.1, Determination of Sample Size](#):

Formerly read: The primary endpoint of the study is mPFS, and the study is powered on the following assumption: a ~~3~~-year mPFS of ~~82.5%~~ for patients in the A+AVD treatment group versus 75% for patients in the ABVD treatment group (HR=0.67 assuming ~~exponential distribution~~). A total of 260 mPFS events will provide 90% power to detect a hazard ratio (HR) of 0.67 at a 1-sided significance level of 0.025. Approximately ~~1040~~ patients will be randomized to achieve 260 mPFS events in ~~about~~ 60 months, assuming 24 months of accrual, a 5% annual dropout rate, and ~~36~~ months of mPFS follow-up after last patient in.

---

Now reads: The primary endpoint of the study is mPFS, and the study is powered on the following assumption: a 2-year mPFS of **81%** for patients in the A+AVD treatment group versus **73%** for patients in the ABVD treatment group (HR=0.67; assuming a **decrease in the PFS event rate after 2 years**). A total of 260 mPFS events will provide 90% power to detect a hazard ratio of 0.67 at a 1-sided significance level of 0.025 **using a log-rank test**. Approximately **1240** patients will be randomized to achieve (**with 95% probability**) 260 mPFS events in **approximately** 60 months, assuming **36** months of accrual, a 5% annual dropout rate, and **24** months of mPFS follow-up after last patient in.

---

- Align the timing of the interim overall survival analysis with that for the final mPFS analysis.

The primary change occurs in Section [8.1.6.2, Analyses of Secondary Efficacy Endpoints](#):

Deleted text: An OS interim analysis will be performed at the time of the final mPFS analysis (~~approximately 3 years after the last patient is enrolled~~), and the final analysis of OS will be performed when 112 deaths have occurred, assuming 5-year OS rates for the A+AVD and ABVD arms are 91% and 88%, respectively (HR=0.75).

Section [8.1.10, Interim Analyses](#) also contains this change.

---

- Revise the timing for the final analysis of overall survival.

The primary change occurs in Section [4.1, Overview of Study Design](#):

Formerly read: The final analysis of OS will be conducted when 112 deaths occur, approximately ~~5~~ years after randomization of the last patient.

---

Now reads: The final analysis of OS will be conducted when 112 deaths occur, approximately **4** years after randomization of the last patient.

Sections that also contain this change are:

- [Section 4.3, Duration of Study](#)
  - [Protocol Summary](#)
- 

**Purpose:** Institute minor modifications in protocol language to improve protocol clarity and compliance, and align study conduct with the sponsor's current guidelines and practices.

- Clarify and align the posttreatment follow-up assessments for PFS disease status, event-free survival, and overall survival.

The change occurs in the [Schedule of Events](#), footnotes a and j:

**Brentuximab vedotin (ADCETRIS®)**

**Clinical Study Protocol C25003 Amendment 7, EudraCT: 2011-005450-60**

Added text: a. Note: Radiological assessments are only required every 12 weeks ( $\pm 1$  week) until 12 months of PTFU and then every 6 months until study closure. **To assist with scheduling of visits, patients may begin to align the timing of their follow-up visits with the timing of CT scans during PTFU, when applicable.**

...

j. Response to treatment and disease assessments...

...

- During the follow-up period: every 3 months for the first year and then every 6 months thereafter. **The CT scan time points are calculated from C1D1.**

- 
- Clarify the PK sampling time points for the 50-patient subset in both treatment arms by correcting the study day stated in the protocol.

The primary change occurs in Section 7.4.19, [Pharmacokinetic Measurements](#); Table 7-1.

	Cycle	Study Day	Time	Window	Relative Time
Formerly read:		7	168 hr	$\pm 24$ hr	End of brentuximab vedotin infusion
Now reads:		8	168 hr	$\pm 24$ hr	End of brentuximab vedotin infusion or End of dacarbazine infusion

The [Schedule of Events](#) also contains this change.

- 
- Update the contact information for product complaints and medication errors.

The change occurs in Section 11.11, [Product Complaints and Medication Errors](#):

Formerly read: Individuals who identify a potential product complaint situation should immediately contact PPD (see below) and report the event.

...

Individuals who identify a potential medication error situation should immediately contact PPD (see below) and report the event.

For Product Complaints or Medication Errors,  
call PPD at  
PPD  
(US and International)

Now reads: Individuals who identify a potential product complaint situation should immediately contact **PPD** (formerly **PPD**) (see below) and report the event.

...

Individuals who identify a potential medication error situation should immediately contact **PPD** (see below) and report the event.

For Product Complaints or Medication Errors,  
call **PPD** at  
**PPD** Option 1 (toll free)  
or  
**PPD** (non-toll free)

- Add the Global Statistical Lead to the list of approvers for the amended protocol.

The change occurs on the Title Page:

Added text:

IRB	institutional review board
IRF	independent review facility
ITT	intent-to-treat
IV	intravenous; intravenously
IVRS	interactive voice response system
MedDRA	Medical Dictionary for Regulatory Activities
Millennium	Millennium Pharmaceuticals, Inc., and its affiliates
mPFS	modified progression-free survival
MRI	magnetic resonance imaging
MRU	medical resource utilization
NCI	National Cancer Institute
NCI CTCAE	National Cancer Institute Common Terminology Criteria for Adverse Events
OS	overall survival
PD	progressive disease (disease progression)
PFS	progression-free survival
PK	pharmacokinetic(s)
PR	partial response
PRO	patient-reported outcome
QALY	quality-adjusted life year
QOL	quality of life
QTc	rate-corrected QT interval (millisec) of electrocardiograph
SAE	serious adverse event
SD	stable disease
$t_{1/2}$	half-life
T_{max}	first time to maximum plasma concentration
ULN	upper limit of the normal range
V_z	volume of distribution in the terminal phase
WHO	World Health Organization

1. INTRODUCTION

In general, the purpose of the Statistical Analysis Plan (SAP) is to provide a framework that addresses the protocol objectives in a statistically rigorous fashion, with minimized bias or analytical deficiencies. Specifically, this plan has the following purpose:

To prospectively (a priori) outline the types of analyses and data presentations that will address the study objectives outlined in the protocol, and to explain in detail how the data will be handled and analyzed, adhering to commonly accepted standards and practices of biostatistical analysis in the pharmaceutical industry.

1.1 Study Design

This open-label, randomized, 2-arm, multicenter, phase 3 study has the primary objective of comparing the modified progression-free survival (mPFS) obtained with A+AVD against that obtained with ABVD.

Approximately 1240 patients will be randomized 1:1 into 2 treatment arms:

- A+AVD: Doxorubicin 25 mg/m², vinblastine 6 mg/m², dacarbazine (DTIC) 375 mg/m², brentuximab vedotin 1.2 mg/kg
- ABVD: Doxorubicin 25 mg/m², bleomycin 10 units/m², vinblastine 6 mg/m², dacarbazine (DTIC) 375 mg/m²

ABVD and A+AVD will be administered intravenously on Days 1 and 15 of each 28-day cycle. Brentuximab vedotin will be administered intravenously over 30 minutes at a dose of 1.2 mg/kg; the brentuximab vedotin infusion is to be started within approximately 1 hour after completion of AVD therapy. Patients may receive up to 6 cycles of therapy (ABVD or A+AVD).

Randomization will be stratified by region (Americas versus Europe versus Asia), and number of International Prognostic Factor Project (IPFP) risk factors (0-1 versus 2-3 versus 4-7).

1.2 Study Objectives

Primary Objective:

- To compare the modified progression-free survival (mPFS) obtained with brentuximab vedotin plus AVD (abbreviated A+AVD) versus that obtained with ABVD for the frontline treatment of advanced classical HL

Key secondary objective:

- To determine if A+AVD improves overall survival (OS) versus that obtained with ABVD

Other secondary objectives:

- To determine if A+AVD improves complete remission (CR) rate at the end of randomized regimen versus that obtained with ABVD
- To determine the safety profile of A+AVD relative to that of ABVD
- To determine the event-free survival (EFS) obtained with A+AVD and ABVD
- To determine the disease-free survival (DFS) obtained with A+AVD and ABVD
- To determine if A+AVD improves overall objective response rate (ORR, defined as CR + PR) versus that obtained with ABVD
- To determine the duration of response (DOR) and duration of complete response (DOCR) obtained in the A+AVD and ABVD arms
- To determine the rate of patients receiving irradiation for HL not in CR in the A+AVD and ABVD arms
- To determine the rate of patients in CR at the end of frontline therapy in the A+AVD and ABVD arms
- To determine the rate of Cycle 2 PET negativity in patients treated with A+AVD versus those treated with ABVD

**Brentuximab vedotin (ADCETRIS™)
Statistical Analysis Plan, Study C25003**

- To determine if A+AVD improves health-related quality of life (HRQoL) versus ABVD
- To describe the PK of brentuximab vedotin, MMAE, and total antibody (TAb) in blood
- To determine the immunogenicity of brentuximab vedotin

Exploratory objectives:

- To investigate any differences in lung-specific patient reported outcomes (PRO) between the treatment arms
- To assess any impact of brentuximab vedotin dosing on serum concentrations of AVD
- To investigate any differences between the treatment arms in the rate of patients alive without HL at 3 and 5 years
- To assess changes in tumor biomarker expression before and after treatment
- CCI [REDACTED]
[REDACTED]
[REDACTED]
- To assess other PROs
- To assess medical resource utilization
- To assess fertility

2. POPULATIONS FOR ANALYSIS

2.1 Intent-to-Treat Population

The Intent-to-Treat (ITT) population will include all patients randomized to treatment. All patients in the ITT population will be analyzed according to the treatment they were randomized to receive and not according to what they actually received, if different. The

**Brentuximab vedotin (ADCETRIS™)
Statistical Analysis Plan, Study C25003**

ITT population will be used for all efficacy analyses of efficacy endpoints unless specified otherwise.

2.2 Per-Protocol Population

The Per-Protocol (PP) population will include all randomized patients who do not have major protocol violation as determined by the project clinician. All decisions to exclude patients from the PP population will be made prior to database lock.

The PP population will be used as a supplement to the analysis of the ITT population for the primary efficacy endpoint.

All patients in the PP population will be analyzed according to the actual treatment received. The PP population will be used as supportive analysis for the primary efficacy endpoint mPFS.

2.3 Response-Evaluable Population

The response-evaluable population is defined as the subset of the ITT population with diagnosis as confirmed by an independent pathology review facility, with measurable disease at baseline, who receive at least 1 dose of study drug, and have at least 1 postbaseline response assessment. The response-evaluable population will be used for the analyses of CR rate, overall response rate, and duration of response.

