## **Brentuximab vedotin (ADCETRIS®)**

### **Clinical Study Protocol C25003 Amendment 7, EudraCT: 2011-005450-60**

between the 2 treatments will also be provided. ORR per IRF will be analyzed based on the ITT population.

Similar analyses will be conducted to compare the rate of patients that received consolidating irradiation between the 2 treatment arms.

CR rate at the end of frontline therapy will be assessed similarly to CR rate at the end of treatment with randomized regimen.

DOR in subjects with confirmed response is the time between first documentation of response and disease progression. DOCR in subjects with confirmed CR is the time between first documentation of CR and disease progression. DOR and DOCR per IRF will be analyzed based on the ITT population.

EFS is defined as the time from randomization until any cause of treatment failure: disease progression, premature discontinuation of treatment for any reason, or death due to any cause, whichever occurs first. Analyses of EFS will be performed based on the ITT population.

DFS is defined as the time from CR to disease progression or to death from lymphoma or acute toxicity from treatment. Analyses of DFS will be performed based on the subset of the ITT population achieving a CR.

The same analyses will be applied to these time-to-event endpoints as those described for OS above.

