5.8 Efficacy Analyses

All efficacy evaluations will be conducted using the ITT population unless otherwise specified.

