5.8.4.2 Complete Remission Rate at the End of Randomized Regimen per IRF

CR rate per IRF is defined as the proportion of patients who achieve CR at the end of treatment with randomized regimen (ABVD or A+AVD) as determined by an IRF.

The number and percentage of patients who experienced a CR at the end of treatment with ABVD/A+AVD will be summarized by treatment groups. The response rates between the 2 treatment groups will be tested using Cochran-Mantel-Haenszel (CMH) chi-square test, stratified by the stratification factors (Section 5.2). The CMH chi-square p-value and the relative risk (and odds ratio), along with its 95% 2-sided CI will also be provided. In

**Brentuximab vedotin (ADCETRIS™)
Statistical Analysis Plan, Study C25003**

addition, the absolute treatment difference in CR response rates will be provided along with the 95% 2-sided CI.

In addition, a logistic regression model will be used to further evaluate the treatment effects on CR rate after adjusting for some prognostic factors. Besides treatment and the stratification factors (Section 5.2), the following prognostic factors will be included in the model simultaneously: age, race (white, non-white), baseline ECOG score, baseline cancer stage, baseline B symptoms, and PET results from Cycle 2. The odds ratio and its associated 95% CIs will be presented. Subgroup analyses may be performed using subgroups defined for mPFS analyses. Additional exploratory analyses may be performed if deemed necessary.

In the primary analysis of CR using ITT population, nonevaluable patients will be treated as nonCR. Sensitivity analyses for CR per IRF will be performed using the response-evaluable population. CR rate per investigator will also be analyzed similarly using the ITT population.

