5.8.4.7 Duration of Response (DOR) or Complete Response (DOCR)

DOR in subjects with confirmed response is the time between first documentation of response (PR or CR) and disease progression. DOCR in subjects with confirmed CR is the time between first documentation of CR and disease progression. DOR and DOCR per IRF will be analyzed based on the subset of ITT population who had response. DOR and DOCR are time-to event-variables.

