6. CHANGES TO PLANNED ANALYSES FROM PROTOCOL

Not applicable

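### SAP 2.3 gives CR rate, ORR and DOR to the response-evaluable population, against the protocol's ITT rule and the SAP's own endpoint sections, and leaves the ORR denominator unsettled

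*SAP*

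**What the plan says.** SAP 2.3 defines the response-evaluable population as ITT patients with a diagnosis confirmed by independent pathology review and measurable disease at baseline, "who receive at least 1 dose of study drug, and have at least 1 postbaseline response assessment". It then says: "The response-evaluable population will be used for the analyses of CR rate, overall response rate, and duration of response". It does not describe this use as supportive or as a sensitivity analysis.

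The other statements point to ITT:

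- **Defaults.** SAP 2.1: "ITT population will be used for all efficacy analyses of efficacy endpoints unless specified otherwise". SAP 5.8: "All efficacy evaluations will be conducted using the ITT population unless otherwise specified". Protocol 8.1.6 has the same default. All three allow exceptions.
- **CR.** Protocol 8.1.6.2 uses ITT, with the response-evaluable set for sensitivity analyses. SAP 5.8.4.2 agrees: "In the primary analysis of CR using ITT population, nonevaluable patients will be treated as nonCR".
- **ORR.** Protocol 8.1.6.2: "ORR per IRF will be analyzed based on the ITT population". SAP 5.8.4.6 defines ORR and classes it as a binary variable, but names no population.
- **DOR and DOCR.** Protocol 8.1.6.2 defines them in confirmed responders and analyses them in ITT. SAP 5.8.4.7: "DOR and DOCR per IRF will be analyzed based on the subset of ITT population who had response".
- **Deviations.** Protocol 8.1 requires departures from its analyses to be indicated in the SAP. The whole entry in SAP 6 is "Not applicable".

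**The concern.** The SAP gives two answers to one question: who is in the denominator. Section 2.3 gives one, and the protocol and the SAP's endpoint sections give the other. With no deviation declared, either the sentence in 2.3 or the entry in SAP 6 is wrong.

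Two of the membership conditions, a dose received and a postbaseline assessment, arise after randomization. The Schedule of Events places the first postbaseline scan at Cycle 2 Day 25. Patients who die or withdraw before then without a scan would leave the response-evaluable denominator; under the ITT rule for CR they count as failures. The trial is open-label, so early losses may differ between arms. Improvement in ORR is a comparative objective, and SAP 3.1 says that hypotheses for secondary endpoints will be tested. If the denominator is settled only after the data are seen, the choice can affect that comparison.

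**Working it through.** **1. Population statements side by side**

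| Endpoint | Protocol 8.1.6.2 | SAP 2.3 | SAP endpoint section |
|---|---|---|---|
| CR, end of randomized regimen | ITT; response-evaluable as sensitivity | Response-evaluable | 5.8.4.2: ITT, nonevaluable = nonCR; response-evaluable as sensitivity |
| ORR | ITT | Response-evaluable | 5.8.4.6: none named |
| DOR | ITT, defined in responders | Response-evaluable | 5.8.4.7: ITT responders |

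For CR and DOR, the specific endpoint section contradicts 2.3 and matches the protocol. For ORR, no such section exists to do so.

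**2. Do the remaining SAP clauses settle ORR?**

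- The ITT defaults in 2.1 and 5.8 give way where something else is specified, and 2.3 can be read as specifying something else.
- SAP 5.8.4.1 gives binary endpoints the same statistical methods as CR in 5.8.4.2, which points to ITT. But it speaks of methods, and the rule in 5.8.4.2 is worded for CR alone.
- The SAP does not rely on that kind of cross-reference to fix a population. Time-to-event endpoints are sent to the OS section, which uses ITT, yet DFS (5.8.4.5) and DOR (5.8.4.7) state their own subsets.
- The section just before 2.3 labels the per-protocol set a supplement and supportive. Section 2.3 carries no such label.

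The text leans towards ITT, but two programmers could defend different ORR denominators.

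**3. Size**

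The plan states no response rate or nonevaluable rate for these analyses, so there is no figure of its own to reproduce. The only input from the documents is n = 620 per arm (protocol 4.1). Everything else here is assumed.

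Let m be the nonevaluable fraction, and assume 90% response among evaluable patients. Then, with counts rounded to whole patients:

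- evaluable E = 620 × (1 − m)
- responders R = 0.90 × E
- response-evaluable ORR = R / E
- ITT ORR = R / 620, with nonevaluable patients as non-responders

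*Within one arm:*

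| m | E | R | R/E | R/620 | Gap (points) |
|---|---|---|---|---|---|
| 1% | 614 | 553 | 90.1% | 89.2% | 0.9 |
| 2% | 608 | 547 | 90.0% | 88.2% | 1.7 |
| 5% | 589 | 530 | 90.0% | 85.5% | 4.5 |
| 10% | 558 | 502 | 90.0% | 81.0% | 9.0 |

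*Between arms with unequal m:* z = d / √(p̄(1 − p̄) × 2/620), unstratified, where d is the ITT difference and p̄ the pooled ITT rate.

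- **2% vs 5%.** Response-evaluable: 547/608 = 90.0% and 530/589 = 90.0%, no difference. ITT: 547/620 = 88.2% and 530/620 = 85.5%, so d = 17/620 = 2.7 points. With p̄ = 1077/1240, z = 1.43 and 2-sided p is about 0.15.
- **3% vs 8%.** Response-evaluable: 541/601 = 90.0% and 513/570 = 90.0%, no difference. ITT: 541/620 = 87.3% and 513/620 = 82.7%, so d = 28/620 = 4.5 points. With p̄ = 1054/1240, z = 2.23 and 2-sided p is about 0.03.

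Nothing in the documents says which arm would lose more patients early, so the direction is open.

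**The case against.** The strongest reply is that 2.3 is loose wording and changes no analysis. It does not say that its set is primary or replaces ITT, and it can be read as a list of the analyses in which the set appears. For CR that use is the sensitivity analysis in 5.8.4.2. SAP 5.8.4.1 refers ORR to the CR methods, the protocol assigns ORR to ITT by name, and SAP 6 declares no change. ORR is also an other secondary endpoint, outside the mPFS-then-OS testing sequence.

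Much of this stands, and it rules out four stronger readings that a reader might infer:

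- *That 2.3 overrides ITT, so ORR will drop patients.* The documents show an unreconciled conflict. With 5.8.4.1 in the SAP, could drop is as far as the text goes.
- *That DOR has three different populations.* The protocol's wording, confirmed responders analysed in ITT, is in substance what 5.8.4.7 says. Only 2.3 differs. Responders already have a postbaseline assessment, so losing patients without one cannot arise for DOR.
- *That the futility CR analysis is equally ambiguous.* SAP 4.1 defines its cohort and expressly includes patients who discontinued. CR at the end of frontline therapy is a binary endpoint, which 5.8.4.1 refers to the ITT rule for CR.
- *That a shift in ORR can be measured against the 5-point futility criterion.* That criterion applies to CR rate.

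The reply does not remove the conflict. The sentence in 2.3 is unqualified, the defaults yield to exceptions, and 5.8.4.1 speaks of methods and not of a population.

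**Conclusion.** The point holds as a conflict between passages. SAP 2.3 disagrees with the protocol for CR rate, ORR and DOR, with SAP 5.8.4.2 for CR and with SAP 5.8.4.7 for DOR, and no deviation is declared. CR at the end of the randomized regimen and DOR have endpoint sections that state the intended population. ORR does not, so its denominator is unsettled.

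If 2.3 were followed, ORR would be computed on a set selected partly after randomization. The consequence depends on nonevaluable rates that the documents do not give. Under the assumptions above, the choice of population moves the between-arm ORR difference by about 2.7 to 4.5 points; equal nonevaluable rates would shift the level in both arms alike. The primary endpoint, the key secondary endpoint, the event target and the type I error are not affected. This should be corrected before database lock, but it does not threaten the trial's main conclusion.

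**What to change.** - **SAP 2.3:** reword the last sentence so that the population *will be used for sensitivity analyses of CR rate and ORR*. Remove DOR, since 5.8.4.7 already states ITT responders.
- **SAP 5.8.4.6:** add that ORR is *analysed in the ITT population, with nonevaluable patients counted as non-responders*.
- **If the response-evaluable set really is meant to be the main set for any of these endpoints:** declare and justify that in SAP 6, as protocol 8.1 requires.

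The cost is SAP wording only. No design figure changes. Reported ORR may be slightly lower than on the response-evaluable denominator.
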